6.3 Study Size

There will be 40 zirconia crowns and 40 ceramic onlays placed. The sample size is according to the international standard represented by the criteria of the American Dental Association (ADA, Council on Scientific Affairs: Acceptance Program Guidelines "Restorative Materials", March 1996). 60 patients will be enrolled in the study.

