Furthermore he/she will check the availability, completeness, logicalness, accuracy and legibility of certain study documents, the CRFs and the Adverse Event/Incident forms. The occurrence of any new Adverse Event/Adverse Device Effect/(near) incident will be reported in the monitoring report and copies of the forms will be collected. Certain data in the CRFs will be verified with source documents (patient files).

The study will be monitored at appropriate intervals by the study monitor, or his/her designee, by means of visits to the study site to evaluate study data and any photographs. Study monitoring visits will involve review of the study status and any issues pertaining to it. All Informed Consent forms, HIPAA forms will be reviewed for signatures; all CRF's will be reviewed for completeness of data entry and that the study protocol is being followed; the subjects'

profiles will be checked to ensure they meet the inclusion and exclusion criteria. Materials will be checked for adequate storage and sufficient quantity to meet the study needs.

Data collection and Data corrections

During monitoring, CRFs will be checked for accuracy, legibility, logicalness and completeness, that all patients have given informed consent, meet selection criteria, and have had treatments randomly allocate in accordance with the study protocol. Resulting changes in the data will be initialized and dated by the person who changed them. If all open questions could be cleared with the investigator, copies of the signed Adverse Event/Incident forms will be provided for the Study Monitor's file. Data entry will be done by [REDACTED], Research Clinic Coordinator of the Cariology, Restorative Sciences Clinical Research Unit.

8 Statistical Analysis

In general, all analyses will be conducted separately by type of restoration; onlay or crown. Means and standard deviations were calculated for all clinical measurements and assessments. Categorical variables were summarized in frequency distributions.

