There will be two datasets analyzed at each recall period; (1) one dataset consisting of subjects who were enrolled up to and including that recall period, and (2) one dataset consisting of all subjects with baseline data. In the second dataset (2) primary and secondary outcome variables which are missing will be imputed using the method of last observation carried forward (LOCF), wherein the last observed values for that variable will be carried forward to all remaining timepoints.

The primary analysis for this study will be the percent of intact/surviving restorations from baseline to the end of each recall period. This will be estimated using the Kaplan-Meier method, there will be no direct comparisons within this analysis. The median survival time of a restoration will be presented alongside survival curves.

The secondary analyses for this study will relate to the FDI criteria for esthetic properties including surface luster, surface staining, margin staining, color match and translucency; functional properties including anatomical form, material fracture, retention,

margin adaptation, occlusal contour and wear, and proximal contact and contour; and biological properties including post-operative sensitivity, caries, gingival index, and plaque index (see Appendix for FDI criteria description). The FDI criteria will be assessed at each recall period versus their respective baseline scores for a particular restoration within a particular subject. FDI criteria which are measured in an ordinal-discrete manner will be assessed using the Wilcoxon-signed rank test. Criteria which are measured continuously such as PI and GI will be assessed using the student's t-test, in the event that the PI and GI scores do not appear to be Normally distributed this assessment will shift to be done using the Wilcoxon-signed rank test.

A two-sided alpha of 0.05 will be used for all comparisons. There will be no adjustments made for multiplicity.

All statistical analyses will be performed e.g. using SAS version 9.4 or above (SAS Institute, Cary, NC).

9 Project Time Line

The recruitment of patients and clinical placement of restorations will begin immediately upon approval and funding of the project. It is anticipated to take 9-12 months to recruit and place the restorations required for the study.

Protocol Amendments and Discontinuing the Study

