1. Clinically excellent / very good	5a.1 No fractures / cracks	5b.1 Restoration in place	6.1 Harmonious outline, margins not detectable
2. Clinically good	5a.2 Small hairline crack.	n.a.	6.2 margins detectable: Slight ditching, slight step/flashes, minor irregularities.
3. Clinically sufficient / satisfactory (minor shortcomings, no unacceptable effects but not adjustable w/o damage)	5a.3 Two or more or larger hairline cracks and/or material chip fracture not affecting the marginal integrity or approximal contact.	n.a.	6.3 moderate detectability: Major irregularities, ditching or flash, steps or minor crevice formation
4. Clinically unsatisfactory / (but repairable)	5a.4.1 Material chip fractures which damage marginal quality or approximal contacts	n.a.	6.4.1 major crevice formation 6.4.2 Larger irregularities or steps (repair necessary)
5. Clinically poor (replacement necessary)	5a.5multiple fractures	5b.5 Complete Loss of restoration	6.5 Generalized major gaps/crevice formation or irregularities.

B. Functional properties	7. Occlusal contour and wear	8. Approximal anatomical form a. contact point b. contour
1. Clinically excellent / very good	7.1 No evidence of occlusal wear, wear equivalent to enamel	8a.1 Normal contact point (floss or 25 µm metal blade can pass) 8b.1 Normal contour.
2. Clinically good	7.2 Evidence of local facet formation < 2.0 mm in diameter, no change in occlusal anatomy, wear only slightly different from that to enamel	8a.2. Contact slightly too strong but no disadvantage (floss or 25 µm metal blade can only pass with pressure). 8b.2 Slightly deficient contour.
3. Clinically sufficient / satisfactory (minor shortcomings, no unacceptable effects but not adjustable w/o damage)	7.3 Evidence of local facet formation > 2.0 mm in diameter, slight change in occlusal anatomy, Different wear rate compared to enamel	8a.3. Somewhat weak contact, no indication of damage to tooth, gingiva or periodontal structures; 50 µm metal blade can pass 8b.3 Visible deficient contour
4. Clinically unsatisfactory / (but repairable)	7.4 Evidence of generalized facet formation with evidence of generalized wear altering occlusal anatomic form, Wear considerably exceeds normal enamel wear	8a.4 Too weak and possible damage due to food impaction; 100 µm metal blade can pass 8b.4 Inadequate contour Repair possible.

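### The only planned inference for each ordinal FDI criterion is a signed-rank test that, when changes are few and one-directional, reflects how many restorations changed and not how badly

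*Combined protocol and SAP*

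**What the plan says.** Section 8 (Statistical Analysis) makes the FDI criteria the secondary analyses. Each criterion is compared at each recall with the same restoration's baseline score, and "FDI criteria which are measured in an ordinal-discrete manner will be assessed using the Wilcoxon-signed rank test". The plan adds that "A two-sided alpha of 0.05 will be used for all comparisons" and that "There will be no adjustments made for multiplicity". Because "all analyses will be conducted separately by type of restoration; onlay or crown", and Section 6.3 states that "There will be 40 zirconia crowns and 40 ceramic onlays placed", each test has at most 40 pairs.

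The plan gives no clinically relevant FDI change, no cut between acceptable and unacceptable grades, and no confidence interval for any criterion. It does not say whether the test is exact or approximate, or how unchanged pairs are handled.

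The Appendix grades most criteria from 1 to 5, with 4 meaning unsatisfactory but repairable and 5 meaning poor, with replacement needed. Retention has only the two end grades: "5b.1 Restoration in place" and "5b.5 Complete Loss of restoration".

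Failures also enter elsewhere. The primary analysis in Section 8 is a Kaplan-Meier estimate of the percentage intact or surviving, without comparison, and categorical variables are tabulated as frequencies.

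**The concern.** Aim 3 (Section 5) asks how the restorations perform clinically over three to five years. The FDI scores are the detailed evidence for that, and the signed-rank p-value is the only inference planned for each ordinal criterion.

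A restoration in place at baseline must score 1 on Retention, so any later change is a worsening of four grades. On other criteria a new restoration may also score 1 or close to it, although the documents give no expected baseline scores. Where most pairs are unchanged and the rest all worsen, the signed-rank test has little to rank: losing a restoration and a minor loss of lustre count alike. A p-value above 0.05 could then sit beside a substantial loss rate, and one below 0.05 beside a criterion on which every restoration is still clinically good.

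**Working it through.** **The plan's own figure.** The 40 per type cannot be reproduced. Section 6.3 says "The sample size is according to the international standard represented by the criteria of the American Dental Association" and gives no effect size, rate or power, so nothing shows what the FDI tests were meant to detect.

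**Inputs.** At most 40 pairs per test (Sections 6.3 and 8); two-sided alpha 0.05 without adjustment (Section 8); Retention grades 1 and 5 only, and grade 2 clinically good on criteria that have it (Appendix). Assumptions: all 40 restorations are assessed and treated as independent, and all changes on the criterion go one way.

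**Exact test.** With k non-zero differences of the same sign, only two of the 2^k sign patterns are as extreme as the one observed, so p = 2 × (1/2)^k whatever the size of the differences.

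- k = 4: 2 × (1/2)^4 = 0.125
- k = 5: 2 × (1/2)^5 = 0.0625
- k = 6: 2 × (1/2)^6 = 0.03125

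Five losses (1 to 5) and five one-grade shifts (1 to 2) both give 0.0625. Six of either give 0.03125. Ranking the zeros by Pratt's method leaves these exact values unchanged.

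**Normal approximation with tie correction.** For k equal changes each rank is (k + 1)/2. The rank sum exceeds its null mean by k(k + 1)/4, and the null SD is (k + 1)√k/4, so z = √k.

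- k = 5: excess 7.5, SD 3.354, z = 2.236, p = 0.025. With continuity correction, z = 7.0/3.354 = 2.087, p = 0.037.
- k = 6: excess 10.5, SD 4.287, z = 2.449, p = 0.014. With continuity correction, z = 10.0/4.287 = 2.333, p = 0.020.

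Five losses are therefore non-significant on the exact test and significant on the approximation. In both versions five losses and five one-grade shifts have the same p-value.

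**What a proportion with an exact (Clopper-Pearson) interval shows.**

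- 4 of 40 lost: 10%, 95% CI 2.8% to 23.7% (exact signed-rank p = 0.125).
- 5 of 40 lost: 12.5%, 95% CI 4.2% to 26.8% (p = 0.0625).
- 6 of 40 moving from 1 to 2: 0 of 40 at grades 4 to 5. The upper limit is 1 − 0.025^(1/40) = 8.8% (p = 0.031).

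**Sensitivity of the exact test to rate.** It needs at least 6 changed restorations out of 40. The binomial probability of 6 or more is 0.38 at a true rate of 12.5% and 0.84 at 20%.

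**Sensitivity to mixed changes.** Five 4-grade worsenings plus one 1-grade worsening on the same criterion give an exact p of 0.031. Six one-grade worsenings plus one one-grade improvement give 0.125.

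**The case against.** - **Failures are already reported.** This stands. With 5 of 40 lost and no censoring, the primary analysis shows 35/40 = 87.5% survival (exact 95% CI 73.2% to 95.8%), and the frequency tables show the grades. A reader might infer that failures could go unseen; the documents do not support that. The cover is incomplete per criterion, though: Section 8 does not tie intact or surviving to FDI grades, so a grade 4 for margins or caries need not be an event, and the tables carry no interval.
- **The test version is open.** This stands. A reader might infer that five losses can never be significant. That is true only of the exact test. Exact calculation is a reasonable expectation with so few non-zero differences, but it is an assumption.
- **A baseline of 1 is documented only by implication, and only for Retention.** This stands. Colour match, anatomical form, contact and margins have grades 2 and 3 that a new restoration could receive, and some scores could improve. The two halves of the contrast also concern different criteria, because Retention has no grade 2.
- **The plan never treats p > 0.05 as proof of stability.** This stands. Such a misreading is a risk to guard against, not something the plan announces.
- **The behaviour is not peculiar to this test.** An exact sign or McNemar test on five one-directional changes also gives 0.0625. That is a reason to report proportions with intervals, not to change to another test.

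**Conclusion.** The point holds as a low-severity weakness in a secondary analysis. For one-directional changes the exact p-value is fixed by the number of changed restorations alone; in the normal approximation the same is true when the changes are equal in size. It therefore says little about the clinical performance named in Aim 3. The size of the problem is the contrast between p = 0.0625 at 12.5% lost (95% CI 4.2% to 26.8%) and p = 0.031 with none of 40 restorations at grades 4 to 5, together with a result for five losses that moves from 0.0625 to 0.025 or 0.037 on an unstated choice of version.

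This rests on 40 assessed, independent restorations and on one-directional change, which is certain for Retention and assumed elsewhere. The documents do not support going further, to a claim that significance is blind to failure in general or that the study would miss its failures.

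**What to change.** In Section 8, for each ordinal FDI criterion, restoration type and recall:

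- Make the main secondary result the number and percentage at grades 4 to 5 with an exact 95% CI. The Appendix already defines these grades as unsatisfactory and poor.
- State the denominator at each recall.
- Count a failed restoration as grade 5 on the criterion on which it failed (for example retention or fracture) at that and later recalls, rather than dropping it or letting LOCF carry an earlier, better score forward. Do not assign 5 on unrelated criteria; a lost crown does not meet the Appendix definition of grade 5 for lustre or caries.
- Note that the interval treats restorations as independent. With 80 restorations in 60 patients and at most two each, 80 − 60 = 20 patients would have two if all 60 are treated. The plan does not say how many of these pairs would be of the same type.
- Keep the signed-rank p-value as supportive, state that it is the exact version and how unchanged pairs are handled, and say that p > 0.05 is not evidence of stable performance.

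The cost is some wording in Section 8 and extra columns in tables already planned, with no new data or visits. The downside is more output and wide intervals, which reflect what 40 restorations per type can show.

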Appendix

Subject Enrollment
Pre-Operative Questionnaire
FDI Clinical Evaluation Criteria
Adverse Event Records

SUBJECT ENROLLMENT

Health Care
EM-11-CR 19-03

University of Michigan School of Dentistry

Inclusion / Exclusion Study Criteria

Review this document with the subject to confirm the inclusion/exclusion criteria qualification.

Inclusion Criteria

Subjects to whom *all* of these conditions apply will be eligible for enrollment in this study:

1. Subject in need of crown and/or onlay restoration
2. Subject age 18 or above
3. Subject with healthy / treated periodontal status (max. degree of movement 1)
4. Subject agrees to participate in the study and signed informed consent and HIPAA form

Exclusion Criteria

Subjects to whom *any* of these conditions apply will be excluded from this study:

1. Devital or sensitive teeth
2. Teeth diagnosed with symptoms of incomplete tooth fracture
3. Teeth with prior endodontic treatment of any kind
4. Teeth with a history of direct or indirect pulp capping procedures
5. Subjects with uncontrolled bruxism or parafunctional habits
6. Subject has known allergies to any product used in this study
7. Subject will not be available for the study duration of 5 years
8. Subjects with significant untreated dental disease to include periodontitis and rampant caries
9. Pregnant or lactating women

Health Care

EM-11-CR 19-03

University of Michigan School of Dentistry

Enrollment

Site Number

Subject Number

Date

 (e.g., 2019-01-23)

Year

Month

Day

Date consented

Year

Month

Day

Inclusion / Exclusion Criteria

Based on the criteria, does this subject qualify for participation in this study? Yes No

If no, check all criteria that were not met below:

Inclusion Criteria 1 2 3 4

Exclusion Criteria 1 2 3 4 5 6 7 8 9

Demographics

Sex Male Female

Age

--	--

 Check if 90 years of age or older

Years

3M
Health Care
EM-11-CR 19-03
University of Michigan School of Dentistry

Date

 Year

 Month

 Day

Pre-Operative Questionnaire

Site Number

Subject Number

Caries Risk Assessment (check one)

- Low (0-1 carious lesions in the last 12 months)
- Moderate (2-4 carious lesions in the last 12 months)
- High (4+ carious lesions in the last 12 months)

Pre-Operative Assessment

1. Tooth to be Restored:

 Onlay Crown
2. Control Tooth Number:

3. Reason tooth needs restoration: (check all that apply)

 Fractured cusp	 Caries
 Esthetics	 Fractured restoration
 Fracture lines	 Open margins
 Severe wear	 Cervical overhang
 Poor contour	 Open proximal contact
4. Pre-operative shade: _____
5. Opposing restorative material: _____
6. Evidence of wear facets on the test tooth: Yes No
7. Evidence of lateral interference(s) on test tooth: Yes No

Comments

FDI CLINICAL EVALUATION CRITERIA

Gingival Index

Gingival score (visual) for gingival area nearest to the restoration margin; evaluate without disclosing.

(Gingival scores will be based upon the standard Loe & Silness Index, 1963)

score 0 = normal gingiva

score 1 = mild inflammation - slight change in color, slight edema, no bleeding

score 2 = moderate inflammation - redness, edema and glazing, bleeding on probing

score 3 = severe inflammation - marked redness and edema, ulceration, spontaneous bleeding

Plaque Index

Plaque score (visual) for facial gingival area nearest to the restoration margin; evaluate without disclosing.

(Plaque scores will be based upon the standard Silness & Loe Index, 1964)

score 0 = no plaque detectable in the gingival area

score 1 = plaque recognized only by running tip of probe across tooth surface at gingival crest

score 2 = moderate accumulation of plaque visible along gingival margin and adjacent tooth

score 3 = abundance of plaque visible along gingival margin and adjacent tooth

A. Aesthetic properties	1. Surface lustre	2a. Surface Staining	2b. Margin Staining
1. Clinically excellent / very good	1.1 Lustre comparable to enamel, Smooth, high gloss surface	2a.1 No surface stain	2b.1 No margin stain
2. Clinically good (after polishing probably very good)	1.2.1 Slightly dull, not noticeable from speaking distance. 1.2.2 Some isolated pores.	2a.2 Minor surface staining, easily removable by gentle polishing (prophy cup)	2b.2 Minor marginal staining, easily removable by gentle polishing (prophy cup)
3. Clinically sufficient / satisfactory (minor shortcomings, no unacceptable effects but not adjustable w/o damage to the tooth)	1.3.1 Dull surface but acceptable if covered with film of saliva. 1.3.2 Multiple pores on more than one third of the surface.	2a.3 Moderate surface staining that may also present on other teeth, not aesthetically unacceptable.	2b.3 Moderate marginal staining, not aesthetically unacceptable.(aggressive removal of surface)
4. Clinically unsatisfactory (but repairable)	1.4.1 Rough or pitted surface, cannot be masked by saliva film, simple polishing is not sufficient. Further intervention necessary. 1.4.2 Voids.	2a.4 Surface stain not removed by gentle polishing, penetrates crown surface, major intervention necessary for improvement. (aggressive removal of material + adding material)	2b.4 Pronounced margin staining, Deeper penetration of the margin, major intervention necessary for improvement. (aggressive removal of material + adding material)
5. Clinically poor (replacement necessary)	1.5 Very rough, unacceptable plaque retentive surface.	2a.5 Severe Subsurface staining within the body of the crown, not accessible for intervention, removed only by replacement of crown	2b.5 Deep and widespread margin staining that penetrates margin, not accessible for intervention removed only by crown replacement

A. Aesthetic properties	3. Colour match and translucency	4. Aesthetic anatomical form
1. Clinically excellent / very good	3.1 Good colour match, no difference in shade and/or translucency.	4.1 Form– comparable to natural tooth anatomy.
2. Clinically good (after polishing probably very good)	3.2 Minor deviations in shade and/or translucency	4.2 Form is only slightly deviated from natural tooth anatomy.
3. Clinically sufficient / satisfactory (minor shortcomings, no unacceptable effects but not adjustable w/o damage to the tooth)	3.3 Distinct deviation but acceptable. Does not affect aesthetics: 3.3.1 more opaque 3.3.2 more translucent 3.3.3 darker 3.3.4 brighter	4.3 Form deviates from the natural anatomy but is aesthetically acceptable.
4. Clinically unsatisfactory (but repairable)	n.a.	4.4. Form is affected and unacceptable aesthetically. Intervention/correction is necessary.
5. Clinically poor (replacement necessary)	3.5 Unacceptable. Replacement necessary.	4.5 Form is unsatisfactory and/or lost. Repair not feasible / reasonable, replacement needed.

B. Functional properties	5a. Fracture of material	5b. Retention	6. Marginal adaptation
1. Clinically excellent / very good	5a.1 No fractures / cracks	5b.1 Restoration in place	6.1 Harmonious outline, margins not detectable
2. Clinically good	5a.2 Small hairline crack.	n.a.	6.2 margins detectable: Slight ditching, slight step/flashes, minor irregularities.
3. Clinically sufficient / satisfactory (minor shortcomings, no unacceptable effects but not adjustable w/o damage)	5a.3 Two or more or larger hairline cracks and/or material chip fracture not affecting the marginal integrity or approximal contact.	n.a.	6.3 moderate detectability: Major irregularities, ditching or flash, steps or minor crevice formation
4. Clinically unsatisfactory / (but repairable)	5a.4.1 Material chip fractures which damage marginal quality or approximal contacts	n.a.	6.4.1 major crevice formation 6.4.2 Larger irregularities or steps (repair necessary)
5. Clinically poor (replacement necessary)	5a.5multiple fractures	5b.5 Complete Loss of restoration	6.5 Generalized major gaps/crevice formation or irregularities.

B. Functional properties	7. Occlusal contour and wear	8. Approximal anatomical form a. contact point b. contour
1. Clinically excellent / very good	7.1 No evidence of occlusal wear, wear equivalent to enamel	8a.1 Normal contact point (floss or 25 µm metal blade can pass) 8b.1 Normal contour.
2. Clinically good	7.2 Evidence of local facet formation < 2.0 mm in diameter, no change in occlusal anatomy, wear only slightly different from that to enamel	8a.2. Contact slightly too strong but no disadvantage (floss or 25 µm metal blade can only pass with pressure). 8b.2 Slightly deficient contour.
3. Clinically sufficient / satisfactory (minor shortcomings, no unacceptable effects but not adjustable w/o damage)	7.3 Evidence of local facet formation > 2.0 mm in diameter, slight change in occlusal anatomy, Different wear rate compared to enamel	8a.3. Somewhat weak contact, no indication of damage to tooth, gingiva or periodontal structures; 50 µm metal blade can pass 8b.3 Visible deficient contour
4. Clinically unsatisfactory / (but repairable)	7.4 Evidence of generalized facet formation with evidence of generalized wear altering occlusal anatomic form, Wear considerably exceeds normal enamel wear	8a.4 Too weak and possible damage due to food impaction; 100 µm metal blade can pass 8b.4 Inadequate contour Repair possible.
5. Clinically poor (replacement necessary)	7.5 Generalized, excessive occlusal wear with loss of anatomic form	8a.5 Too weak and/or clear damage due to food impaction and/or pain/gingivitis. 8b.4 Insufficient contour requires replacement

B. Functional properties	9. Radiographic examination (when applicable)	10. Patient's view
1. Clinically excellent / very good	9.1 No pathology, harmonious transition between restoration and tooth.	10.1 Entirely satisfied with aesthetics and function.
2. Clinically good	9.2.1 Acceptable material excess present. 9.2.2 Positive/negative step present at margin <150 µm.	10.2 Satisfied. 10.2.1 Aesthetics. 10.2.2 Function, e.g., minor roughness

3. Clinically sufficient / satisfactory (minor shortcomings, no unacceptable effects but not adjustable w/o damage)	9.3. 1 Marginal gap < 250 µm. 9.3. 2 Negative steps visible < 250 µm. No adverse effects noticed. 9.3.3 Poor radiopacity of the restoration.	10.3 Minor criticism but no adverse clinical effects. 10.3.1 Aesthetic shortcomings. 10.3.2 Some lack of chewing comfort. 10.3.3 Unpleasant treatment procedure.
4. Clinically unsatisfactory / (but repairable)	9.4.1 Marginal gap >250 µm. 9.4.2 Material excess accessible but not removable. 9.4.3 Negative steps >250µm and repairable.	10.4 Desire for improvement 10.4.1 Aesthetics. 10.4.2 Function, e.g., tongue irritation Reshaping of anatomic form or refurbishing is possible.
5. Clinically poor (replacement necessary)	9.5.1 Secondary caries, large gaps, large overhangs 9.5.2 Apical pathology 9.5.3 Fracture/loss of restoration or tooth.	10.5 Completely dissatisfied and / or adverse effects, incl. pain.

C. Biological properties	11. Postoperative (hyper-) sensitivity and tooth vitality	12. Recurrence of caries (CAR), erosion, abfraction
1. Clinically very good	11.1 No hypersensitivity, normal vitality.	12.1 No secondary or primary caries
2. Clinically good (after correction maybe very good) No treatment required.	11.2 Minor hypersensitivity for a limited period of time, normal vitality.	12.2 Small and localized 1. Demineralization 2. Erosion or 3. Abfraction.
3.Clinically sufficient / satisfactory (minor shortcomings with no adverse effects but not adjustable without damage to the tooth)	11.3.1 Moderate hypersensitivity 11.3.2 Delayed/mild sensitivity; no subjective complaints, no treatment needed.	12.3 Larger areas of 1. Demineralisation 2. Erosion or 3.Abrasion/abfraction, dentine not exposed Only preventive measures necessary.
4. Clinically unsatisfactory (repair for prophylactic reasons)	11.4.1 Intense hypersensitivity. 11.4.2 Delayed with minor subjective symptoms. 11.4.3 No clinical detectable sensitivity. Intervention necessary but not replacement.	12. 4.1 Caries with cavitation and suspected undermining caries 12.4.2 Erosion in dentin 12.4.3 Abrasion/ abfraction in dentin. Localized and accessible can be repaired.
5. Clinically poor (replacement necessary)	11.5 Intense, acute pulpitis or non-vital tooth. Endodontic treatment is necessary, and restoration has to be replaced.	12.5 Deep caries or exposed dentine that is not accessible for repair of restoration.

3M
Health Care
EM-11-CR 19-03
University of Michigan School of Dentistry

**Adverse Event
Record**

AE# Site Number

Subject Number

Date of onset:
Year Month Day

NOTICE: Contact 3M Study Monitor ASAP if the adverse event is serious or unanticipated/unexpected.

Specify the sign or symptom of the adverse event.

Identify study material(s) used at the site of the adverse event. (check all that apply)

 Suglue-3	 ADH-19	 Scotchbond Universal Etchant	 Chairside Zirconia
 CoJet Sand	 Vitrebond Plus Light cure glass ionomer liner/base	 Epilar Deep Cure S	

Other: _____

*Severity at Onset (Check one)	Seriousness (Check one)	Anticipated / Expected (Check all that apply)	Related to Study Material (Check one)	Action Taken (Check all that apply)
 Mild subject is aware of signs, symptoms but they are easily tolerated	 Not serious  Serious a) led to death, b) led to serious deterioration in health that either resulted in: 1) a life-threatening illness or injury, or 2) a permanent impairment of a body structure or a body function, or 3) in-patient or prolonged hospitalization, or 4) medical or surgical intervention to prevent life threatening illness or injury or permanent impairment to a body structure or a body function, c) led to fetal distress, fetal death or a congenital abnormality or birth defect.	 Anticipated / Expected defined in protocol/ Investigational Plan, Investigator's Brochure or Informed Consent form  Unanticipated / Unexpected in nature  Unanticipated / Unexpected in severity	 Not related  Unlikely  Possible  Probable  Causal relationship	 None  Study product discontinued  Withdrawn from study  Medications (describe below)  Other (describe below)
 Moderate signs, symptoms are sufficient to restrict but not prevent subject's daily activity				
 Severe subject unable to perform daily activity				

Outcome (Check one)

 Recovered	Date recovered:     
 Persistent effect (describe below)	Year Month Day
 Death (describe below)	

Describe the chronology of events, actions taken and outcome.

* From onset to outcome, did the adverse event increase in severity? Yes No

If yes, to what degree? Moderate Severe
